#### **3.6. Data Collection**

Following ethics committee approval, eligible patients aged 18–65 years scheduled for elective modified radical mastectomy between April 15 and May 15, 2024, at Hacettepe University Hospital, who had already been assigned ESP or PECS I-II blocks for postoperative pain control independent of the study, will be enrolled. The study is observational, and no interventions will be made regarding clinical treatment decisions. Patient demographic data (ASA score, age, sex, weight, height, BMI, comorbidities) and intraoperative details will be recorded

Postoperative data within the first 24 hours will be collected via face-to-face interviews and entered into the follow-up and DN4 forms. At 3 months, DN2 and SF-12 questionnaires will be administered via telephone interviews

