### 2. Rationale of the Project:

Breast cancer is the most commonly diagnosed cancer among women and remains a leading cause of cancer-related mortality. Globally, it ranks second only to lung cancer in incidence, with both accounting for approximately 11.6% of all diagnosed cancer cases (1). In the United States, the lifetime risk for a woman to develop breast cancer is estimated at 13%, indicating that one in eight women will be affected during their lifetime (2).

Over the past two decades, significant advances in breast cancer research have markedly improved our understanding of the disease, enabling the development of more effective and less toxic treatments. Enhanced public awareness and improved screening methods have facilitated early detection at stages amenable to surgical resection and curative therapy. Consequently, survival rates—especially among younger women—have substantially improved (3).

Surgical treatment of breast cancer includes both conservative and non-conservative approaches. Conservative surgeries account for approximately 40% of all procedures, with quadrantectomy being the most commonly performed among them (4). However, surgical treatment may lead to various complications, including chronic postoperative pain (5).

Post-mastectomy pain syndrome (PMPS) is typically defined as chronic pain in the breast or chest wall persisting for at least three months following cancer treatment. It arises after surgical interventions for breast cancer and is believed to result from primary nerve injury or dysfunction of the nervous system (6,7). Clinically, it presents with features of neuropathic pain such as burning, tingling, stabbing, or shooting sensations, and hyperesthesia (8). Although no standardized diagnostic criteria exist, the estimated incidence ranges from 40% to 50% (7,9), with about half of affected women reporting moderate to severe pain (10).

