Younger age (<40 years) has been identified as a major risk factor, though age does not appear to correlate with the intensity of reported pain (10). Severe acute postoperative pain is also considered a predictive factor for the development of chronic pain. Furthermore, radiotherapy to the breast and/or axillary region has been associated with an increased risk of chronic pain when compared to patients who did not receive radiation therapy (11). Among surgical contributors to PMPS, extensive axillary lymph node dissection is significant due to the increased risk of intercostobrachial nerve injury, which may lead to neuropathic pain (12,13).

Strategies aimed at reducing the risk of PMPS emphasize optimizing perioperative pain management. Techniques such as paravertebral, erector spinae plane (ESP), and pectoral

nerve blocks are routinely applied in appropriate surgical cases to reduce postoperative pain and minimize the risk of chronic pain development in many centers, including ours (14). Both ESP and PECS I-II blocks have demonstrated efficacy and are associated with low complication rates (14,15,16).

In our study, we aim to observe the incidence of chronic pain following mastectomy in patients who have received either a pectoral nerve block (PECS I-II) or an erector spinae plane (ESP) block as part of their pain management strategy. These blocks will be administered by the attending anesthesiologist after general anesthesia induction and prior to the initiation of surgery. The choice and timing of the block will be determined independently by the anesthesiologist and not influenced by the study team. The primary outcome of this study is to compare the incidence of chronic postoperative pain between the two groups. The secondary outcome is to assess the impact of these blocks on acute postoperative pain levels and opioid requirements.

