#### **3.3 Study Population, Sample Size, and Study Groups**

Following approval by the Hacettepe University Ethical Committee, patients aged 18 to 65 years, classified as ASA physical status I-II, and scheduled to undergo elective modified radical mastectomy or simple mastectomy with sentinel/axillary lymph node dissection under general anesthesia at Hacettepe University Hospitals between April 15 and May 15, 2024, will be included. Patients must have already been scheduled to receive either an ESP or PECS I-II block for postoperative pain management independently of the study. A total of 40 patients will be enrolled, with 20 in each group at least. Patients with coagulation disorders, allergies to local anesthetics, obesity ( $BMI > 35 \text{ kg/m}^2$ ), infection at the injection site, pre-existing neurological deficits, or unwillingness to participate, as well as those with failed blocks, will be excluded. The decision to perform blocks is made by the responsible anesthesiologist and will not be influenced by the study team.

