#### **3.5. Research Method and Data Collection Tools:**

Upon admission to the operating room, non-invasive arterial blood pressure, electrocardiogram, and peripheral oxygen saturation monitoring will be conducted before

the induction of general anesthesia. This is the routine monitoring protocol applied prior to anesthesia. All patients will receive standard general anesthesia and standard ventilation modes. The research team will not intervene in the anesthesia procedure.

According to the standard anesthesia practice in these cases, anesthesia induction is performed with propofol (1.5–2.5 mg/kg), rocuronium (0.4–0.6 mg/kg), and fentanyl (1–2 mcg/kg), with a 50% oxygen-air mixture. Standard ventilator settings are applied.

Anesthesia maintenance consists of 2% sevoflurane with 50% oxygen-air mixture. These practices are routine in our operating theater and are not specifically designed for this study. In the event of any non-routine requirement, decisions will be made by the responsible anesthesiologist, without any intervention from the research team. The study will commence after anesthesia induction and block application.

Following the induction of general anesthesia, the responsible anesthesiologist will independently administer either the PECS I-II or ESP block prior to surgical incision. The choice of block will not be influenced by the study and will be determined solely by the anesthesiologist, regardless of group distribution. The research team will not interfere in the selection or method of block administration.

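### Sections 3.3 and 3.6 state eligible surgery differently, and under the 3.3 population a difference in axillary surgery between the block groups could be read as a block effect because the planned comparison is crude

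*Combined protocol and SAP*

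**What the plan says.** **Eligible surgery.** Section 3.3 (Study Population, Sample Size, and Study Groups) includes patients "scheduled to undergo elective modified radical mastectomy or simple mastectomy with sentinel/axillary lymph node dissection under general anesthesia". Section 3.6 (Data Collection) describes those to be enrolled as eligible patients "scheduled for elective modified radical mastectomy between April 15 and May 15, 2024". Both are current text.

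**Prognostic factor.** Section 2 (Rationale of the Project) states: "Among surgical contributors to PMPS, extensive axillary lymph node dissection is significant due to the increased risk of intercostobrachial nerve injury".

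**Primary outcome.** Also in section 2: "The primary outcome of this study is to compare the incidence of chronic postoperative pain between the two groups".

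**Allocation.** The study is a prospective cohort (section 3.4). Section 3.5 says: "The choice of block will not be influenced by the study and will be determined solely by the anesthesiologist".

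**Size.** Section 3.3: "A total of 40 patients will be enrolled, with 20 in each group at least". No power, effect size or allowance for loss is given.

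**Analysis.** Section 3.7 compares categorical variables by chi-square or Fisher's exact test. It plans no stratification or adjustment, whether for surgery or anything else.

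**Recording.** Section 3.6 lists the demographic items one by one but covers surgery only by a general reference to intraoperative details. Neither type of mastectomy nor axillary procedure is named.

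**The concern.** A patient having simple mastectomy with sentinel node surgery is eligible under 3.3 but falls outside the enrolment sentence in 3.6. A protocol should have one answer to whether she enters the study.

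The larger matter is what the 3.3 population implies for the comparison. Four features of the plan combine:

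- axillary extent varies between patients;
- the protocol itself links extensive dissection to the primary outcome;
- nothing in the allocation balances axillary extent between blocks;
- the analysis does not take it into account.

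If one block group happens to contain more extensive dissections, its chronic pain incidence will be higher for a reason unrelated to the block. The planned test would attribute that excess to the block. Nothing in the plan commits the study to showing the imbalance, so a reader of the results might not be able to detect it.

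**Working it through.** **1. The two eligibility statements side by side**

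| Item | Section 3.3 | Section 3.6 |
|---|---|---|
| Operation | Modified radical mastectomy, or simple mastectomy with sentinel/axillary dissection | Modified radical mastectomy |
| Age | 18 to 65 | 18 to 65 |
| Dates | 15 April to 15 May 2024 | Same |
| Hospital | Hacettepe | Same |
| Block already planned | Yes | Yes |
| ASA I-II | Stated | Not stated as a criterion |
| Exclusions | Listed | Not stated |

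The operation is the only item that both sections state and on which they differ. Section 3.6 also leaves out the ASA limit and every exclusion, which suggests a shortened restatement rather than a second definition.

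**2. Size of a possible bias**

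The plan has no figure to reproduce here. If the block has no effect:

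spurious difference = (difference between groups in share with extensive dissection) × (difference in chronic pain risk with and without it).

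Both factors are assumptions; neither is in the documents. Section 2 gives an overall incidence of 40% to 50%, so the risks below are chosen to average 45% in a half-and-half mix.

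| Assumed risk, extensive v not | Risk difference | Mix 60/40 v 40/60 (imbalance 0.2) | Mix 70/30 v 30/70 (imbalance 0.4) |
|---|---|---|---|
| 50% v 40% | 10 points | 0.2 × 10 = 2 | 0.4 × 10 = 4 |
| 55% v 35% | 20 points | 0.2 × 20 = 4 | 0.4 × 20 = 8 |
| 60% v 30% | 30 points | 0.2 × 30 = 6 | 0.4 × 30 = 12 |

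The middle row in full, at 70/30 v 30/70: 0.7 × 55 + 0.3 × 35 = 49% against 0.3 × 55 + 0.7 × 35 = 41%, a difference of 8 points with no block effect.

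**3. Comparison with sampling error**

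95% half-width of a crude risk difference at 20 per group = 1.96 × √(2p(1−p)/20).

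- p = 0.40: 1.96 × √0.0240 = 30.4 points
- p = 0.45: 1.96 × √0.02475 = 30.8 points
- p = 0.50: 1.96 × √0.0250 = 31.0 points

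A bias of 4 to 8 points is therefore about 13% to 26% of the half-width (4/30.8 and 8/30.8). Sampling error dominates. The bias, however, does not average out, and neither the p-value nor the interval reflects it.

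**4. Precision cost of stratifying**

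Take the 55% v 35% row with two strata. The two strata have equal Mantel-Haenszel weights, so the variance is the sum of the stratum variances divided by 4.

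- 60/40 v 40/60 (strata of 12 v 8 and 8 v 12): variances 0.55 × 0.45 × (1/12 + 1/8) = 0.0516 and 0.35 × 0.65 × (1/12 + 1/8) = 0.0474. Half-width 1.96 × √((0.0516 + 0.0474)/4) = 30.8 points, against 30.8 for the crude estimate.
- 70/30 v 30/70 (strata of 14 v 6 and 6 v 14): variances 0.0589 and 0.0542. Half-width 33.0 points, against 30.7 for the crude estimate.

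In these examples the interval widens by at most about 2 points each side.

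**The case against.** **The mismatch is close to clerical.** Section 3.3 is the section that defines the population. Section 3.6 concerns data collection, refers to patients already eligible, and omits the ASA limit and all exclusions. Nobody would suppose those were meant to be dropped. The title and aim speak of mastectomy generally, which fits 3.3. This stands. A reader might infer two competing study populations, but the text does not support that. It does support a needed correction, because 3.6 is the sentence that says who will be enrolled.

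**The bias is not a consequence of the mismatch.** It arises under 3.3 alone and would remain once 3.6 was aligned with it. This also stands, so the figures above measure possible confounding and say nothing about how many patients the narrower wording would remove.

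**Procedure is not the same as axillary extent.** Section 3.3 allows simple mastectomy with axillary dissection, so the documents do not show that dropping simple mastectomies would remove the patients with less axillary surgery. Axillary extent should therefore be the stratifier, rather than mastectomy type.

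**The path is unproven.** A reader might infer that anesthesiologists pick the block according to the planned operation. The protocol says only that they decide. Imbalance is possible because nothing in the allocation prevents it, and in groups of 20 it could also arise by chance.

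**The data may already be collected.** Intraoperative details are to be recorded, and the data form is not among the documents. It cannot be concluded that axillary procedure will go unrecorded, only that the plan does not commit to recording it.

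**Conclusion.** The point holds as a cheap improvement. The two statements of eligible surgery differ and need one definition, with 3.6 most likely an incomplete restatement of 3.3. Under 3.3, axillary extent is a prognostic factor that the protocol itself names and that neither the allocation nor the analysis controls, so an imbalance could pass for a block effect.

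The documents do not give the size. With an assumed 20-point risk difference and an assumed 20 to 40 point imbalance, the spurious difference is 4 to 8 points. With risk differences of 10 to 30 points, it is 2 to 12. All of these lie well inside a 95% half-width of about 30 points, so axillary imbalance is not the main limit on what 40 patients can show.

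Two stronger statements are not supported. Section 2 calls extensive dissection a contributor to chronic pain, so describing it as an established cause of the outcome goes further than the text. Figures of 5 and 10 points from assumed risks of 50% and 25% also fit poorly: a half-and-half mix would give 37.5% overall, below the 40% to 50% that the protocol cites.

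**What to change.** 1. Reconcile section 3.6 with section 3.3 so that eligible surgery has one definition, preferably by having 3.6 refer to 3.3 instead of restating the criteria.
2. Name the axillary procedure (sentinel or axillary dissection) in section 3.6 as a variable recorded for every patient, and tabulate it by block group.
3. In section 3.7, add a Mantel-Haenszel risk difference for chronic pain, stratified by axillary extent, with its 95% confidence interval, reported beside the crude difference. State this before the outcome data are examined.

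The cost is one corrected sentence, one two-category field that should be available from the operation note, and one additional estimate. The stratified estimate is slightly less precise at n = 40, by no more than about 2 points of half-width in the examples worked above. If a stratum holds very few patients in one group, the table by block still lets the reader judge the imbalance.

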### **3.7. Data Analysis**

Normality of numeric data will be assessed using the Shapiro-Wilk test. Data following a normal distribution will be compared between two independent groups using the Student's t-test. Non-normally distributed data will be analyzed using the Mann-Whitney U test. For three-group comparisons, one-way ANOVA will be used if parametric assumptions are met; otherwise, the Kruskal-Wallis H test will be applied. Descriptive statistics will include mean  $\pm$  standard deviation for normally distributed data, or median (minimum–maximum) for non-normal data. Categorical variables will be summarized as counts (percentages), and group comparisons will be performed using chi-square or Fisher's exact test as appropriate. A p-value  $<0.05$  will be considered statistically significant in all analyses.

